 - **The PI and investigators will review the data quarterly for safety issues. No statistical claims are being made with the data being collected, and there is no minimum**

•

- **sample size required.**
 - iii. What will the multi-site process be for protocol modifications?
 - **The PI will request any protocol modifications to be applied to all sites. Protocol amendment will be requested with the need of local IRB acknowledgements to be collected from all sites.**
 - **All the IRB related documentations are kept in the master regulatory binder in the research office. Copies of the PIs curriculum vitae and qualifications are kept in the regulatory binder.**
 - **All sites are required to send their IRB approvals to the central site.**

12. Statistical Considerations: Describe the statistical analyses that support the study design.

A sample size of 3-5 patients per site was selected to allow for a sufficient physician experience to generate an ease of use and efficacy of occlusion determination (target 25 total)
No statistical claims are being made with the data being collected, there is no minimum sample size required.

SECTION VI: RESEARCH INVOLVING DRUGS, BIOLOGICS, RADIOTRACERS, PLACEBOS AND DEVICES

If this section (or one of its parts, A or B) is not applicable, state N/A and delete the rest of the section.

A. DRUGS, BIOLOGICS and RADIOTRACERS N/A

B. DEVICES

1. Are there any investigational devices used or investigational procedures performed at Yale-New Haven Hospital (YNHH) (e.g., in the YNHH Operating Room or YNHH Heart and Vascular Center)? Yes No *If Yes, please be aware of the following requirements:*
 - a. A YNHH New Product/Trial Request Form must be completed via EPIC: **Pull down the Tools tab in the EPIC Banner, Click on Lawson, Click on “Add new” under the New Technology Request Summary and fill out the forms requested including the “Initial**

Request Form,” “Clinical Evidence Summary, “ and attach any other pertinent documents. Then select “save and submit” to submit your request; and

b. Your request must be reviewed and approved **in writing** by the appropriate YNHH committee before patients/subjects may be scheduled to receive the investigational device or investigational procedure.

2. What is the name of the device to be studied in this protocol?

Bridge Occlusion Balloon Catheter.

Has this device been FDA approved? Yes No
If yes, state for what indication.

Bridge Occlusion Balloon received FDA 510(k) clearance on 02/05/2016 for temporary vessel occlusion in cardiac lead extraction procedures (K153530).

Indication: The Bridge Occlusion Balloon catheter is indicated for use for temporary vessel occlusion of the superior vena cava in applications including perioperative occlusion and emergency control of hemorrhage.

Any use for procedures other than those indicated in these instructions is not recommended.

Background Information: Provide a description of previous human use, known risks, and any other factors that might influence risks. If this is the first time this device is being used in humans, include relevant data on animal models.

Five animal studies comprise the pre-clinical data sources. The study IDs are NGX017 (Intravascular Tear Model), NGX021 (Efficacy of Occlusion Balloon Shape), NGX023 (Safety of Occlusion Balloon Deployment), NGX027 (Efficacy of Bridge Occlusion Balloon), and NGX028 (Safety of Bridge Occlusion Balloon).

Results Summary:

Five pre-clinical animal studies were conducted at American Preclinical Services (APS), located in Minneapolis, MN, USA. Three of the animal studies were used to develop the clinical model, and to assess device design and safety. Two of the animal studies were conducted in accordance with FDA GLP regulations to assess the efficacy and safety of the final device design.

All studies were conducted in the porcine animal model due to the anatomical and physiological similarities to the human cardiovascular system. Study results demonstrated that the Bridge Occlusion Balloon significantly reduced blood loss when deployed at the site of a SVC tear, which allowed all animals to be kept in a clinically stable condition for the full

duration of every procedure. Deployment of the Bridge Occlusion Balloon did not produce any clinically significant histological findings or neurological or physical deficiencies. Taken together, these results suggest that the Bridge Occlusion balloon is safe and effective for temporary occlusion of the SVC.

The Bridge occlusion balloon is designed based on human SVC (superior vena cava) measurements to inflate and cover the entire SVC with a single device with a balloon working length of 80mm.

Clamping a patent unobstructed SVC can have adverse hemodynamic consequences such as a sudden drop in mean arterial blood pressure and venous stasis that can induce arrhythmias and/or cardiac arrest. Additional consequences may be cerebral venous hypertension, decrease in cerebral perfusion, and alteration of cerebral arteriovenous gradient leading to brain damage^(1, 2, and 3). While there is limited evidence for temporary balloon occlusion during an SVC tear, the efficacy of temporary venous occlusion to minimize or stop blood flow during a cardiac surgical repair, reconstruction, or a minimally invasive procedural treatment with little to no neurological impairment or cerebral damage has been studied in the literature. Although there is a risk to occluding the SVC, the studies described herein demonstrate that such procedures can be done safely.⁽⁴⁾

Snaring of the caval veins to occlude flow prior to right atrial incision during tricuspid valve surgery is associated with a risk of sudden injury and untreatable bleeding. As an alternative, Foley and Fogarty balloon catheters^(5, 6) and Swan-Ganz⁽⁷⁾ catheters have been described in the use of temporary SVC occlusion. The utility of Swan-Ganz catheter with SVC clamping was described in 7 patients undergoing thoracic surgical SVC reconstruction or replacement with SVC bypass. This system allowed hemodynamic stability with no overall change in blood pressure, heart rate, and oxygen saturation values. In one patient, facial edema and cyanosis was observed during SVC clamping, although this rapidly resolved following SVC reconstruction. Clinical postoperative neurological examination after extubation revealed no neurological impairment or deficit in any patient. One patient presented with severe agitation during awakening and required additional sedation and extubation time. There was no 90 day postoperative mortality. The mean SVC occlusion time was 24±3 minutes in this study.

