- Venogram: pre-occlusion, during occlusion confirming vein occlusion, and post-occlusion to evaluate vein integrity.
- Hemodynamics (BP, HR, and SPO2) at a pre-occlusion baseline, during occlusion, and post-occlusion and recovery time (5min).
- Time to insert, position, and deploy Bridge from sterile packaging.
- Any perioperative and post-24hr clinical complications the PI at each center feels is directly related to deployment of the Bridge occlusion balloon.

Study Endpoints:

Primary Endpoints

- Robust clinical workflow is established
- The Bridge occlusion balloon will:
 - ✓ Fit within an acceptable patient preparation clinical workflow.
 - ✓ Will be easy to insert, position, and deploy in vivo.

- ✓ Will be successful to achieve intact SVC occlusion with the Bridge balloon.

Secondary Endpoints

- Will be easy to recognize via fluoroscopy when occlusion.
- There will be no unacceptable hemodynamics during occlusion or post occlusion.
- There will be no perioperative clinical sequelae related to occlusion of the SVC area with the Bridge occlusion balloon.

Device Description

The Bridge Occlusion Balloon catheter is designed for temporary vessel occlusion of the superior vena cava in applications including perioperative occlusion and emergency control of hemorrhage associated with vascular tears that may occur during lead extraction procedures.

The subject device is packaged in a single sterile barrier system, is provided to the user sterile, and is intended for single use. The device does not include any accessories or additional components. **(Figure.1)** is an illustration of the Bridge Occlusion Balloon catheter. The device consists of a proximal hub, strain relief, catheter shaft, and a distal balloon. Three radiopaque markers are mounted on the catheter shaft inside the balloon. **(Table.1)** lists the dimensional specifications for the device.

Figure 1: Bridge Occlusion Balloon Catheter (top) and with balloon protector (bottom)

[figure not shown]

Table 1: Bridge Occlusion Balloon Specifications

Cat. #	Catheter Length (cm)	Balloon Diameter (mm)	Balloon Length (mm)	Maximum OD (Crossing Profile) (mm/in)	Minimum Tip/Guidewire Lumen ID (mm/in)	Maximum Inflation Volume (cc)
590-001	90	20 nominal 31 at max	80 nominal	4/0.157	0.9/0.036	60

Occlusion Balloon Catheter Description

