11. Data and Safety Monitoring Plan: Include an appropriate Data and Safety Monitoring Plan (DSMP) based on the investigator's risk assessment stated below. (Note: the HIC will make the final determination of the risk to subjects.) For more information, see the Instructions, page 24.

- a. What is the investigator's assessment of the overall risk level for subjects participating in this study?
The risk assessment is greater than minimal.
- b. If children are involved, what is the investigator's assessment of the overall risk level for the children participating in this study?
No children will be enrolled in this study.
- c. Include an appropriate Data and Safety Monitoring Plan. Examples of DSMPs are available here <http://www.yale.edu/hrpp/forms-templates/biomedical.html> for
 - i. Minimal risk
 - ii. Greater than minimal

Greater Than Minimal Risk DSMP

1. Personnel responsible for the safety review and its frequency:

The principal investigator will be responsible for monitoring the data, assuring protocol compliance, and conducting the safety reviews at the specified frequency, which must be conducted at a minimum of every 6 months (including when reapproval of the protocol is sought). During the review process, the principal investigator (monitor) will evaluate whether the study should continue unchanged, require modification/amendment, or close to enrollment. Either the principal investigator, the IRB or have the authority to stop or suspend the study or require modifications.

All sites are required to document all the adverse events and complication in the data collection form with the site PI assessment. Each site will send de-identified source documents to the central site through secured academic email or fax to the central site. The fax is located in a locked office, to which only the research team has access.

Through the remote monitoring plan, the central PI will review all the adverse events and perioperative complication within 1 day of receiving the data collection form. Additional source

documents will be requested from the site. All the source documents will be stored in a locked research office in the cardiology department.

2. The risks associated with the current study are deemed greater than minimal for the following reasons: (choose those that apply)

1. We do not view the risks associated with the Bridge Balloon as minimal risks.

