Although we have assessed the proposed study as one of greater than minimal risk, the potential exists for anticipated and/or unanticipated adverse events, serious or otherwise, to occur since it is not possible to predict with certainty the absolute risk in any given individual or in advance of first-hand experience with the proposed study methods. Therefore, we provide a plan for monitoring the data and safety of the proposed study as follows:

An independent study monitor will have the oversight of the study. A remote monitoring plan is in place to validate the information collected from all sites.

The monitor will receive the documents from each site and will check the accuracy and completeness of the data entries, source documents, and other trial-related records against each other. The monitor specifically will verify that the data required by the protocol are reported accurately on the data collection sheet and are consistent with the source data/documents.

The study monitor will verify that all the adverse events, concomitant medications, and current illnesses are reported in accordance with the protocol. In addition, the monitor will determine whether all adverse events (AEs) are appropriately reported within the time periods.

The appointed monitor will verify that source documents and other trial records are accurate, complete, kept up-to-date, and maintained. Also will verifying that the investigator is enrolling only eligible subjects and report the subject recruitment rate.

The monitor will submit a written report to the sponsor after each monitoring action. The report will include a summary of what the monitor reviewed and the monitor's statements concerning the significant findings, deviations and deficiencies, conclusions, actions taken or to be taken.

Review of documentation will begin for each site after the first subject's data is sent to the coordinating center. The review will take place within 5 days of receipt of the information. The monitor, after reviewing the data, will email the investigator with any queries. When all queries are responded to satisfactorily, the monitor will review additional subjects after the third subject is enrolled at the site.

All the qualification of the appointed monitor will be kept in the master binder.

3. Attribution of Adverse Events:

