Adverse events will be monitored for each subject participating in the study and attributed to the study procedures / design by the principal investigator ([name]) according to the following categories:

- a.) Definite: Adverse event is clearly related to investigational procedures(s)/agent(s).
- b.) Probable: Adverse event is likely related to investigational procedures(s)/agent(s).
- c.) Possible: Adverse event may be related to investigational procedures(s)/agent(s).
- d.) Unlikely: Adverse event is likely not to be related to the investigational procedures(s)/agent(s).
- e.) Unrelated: Adverse event is clearly not related to investigational procedures(s)/agent(s).

4. Plan for Grading Adverse Events:

The following scale will be used in grading the severity of adverse events noted during the study:

- 1. Mild adverse event
- 2. Moderate adverse event
- 3. Severe

5. Plan for Determining Seriousness of Adverse Events:

Serious Adverse Events:

In addition to grading the adverse event, the PI will determine whether the adverse event meets the criteria for a Serious Adverse Event (SAE). An adverse event is considered serious if it results in any of the following outcomes:

- 1. Death;
- 2. A life-threatening experience in-patient hospitalization or prolongation of existing hospitalization;
- 3. A persistent or significant disability or incapacity;
- 4. A congenital anomaly or birth defect; OR
- 5. Any other adverse event that, based upon appropriate medical judgment, may jeopardize the subject's health and may require medical or surgical intervention to prevent one of the other outcomes listed in this definition.

An adverse event may be graded as severe but still not meet the criteria for a Serious Adverse Event. Similarly, an adverse event may be graded as moderate but still meet the criteria for an SAE. It is important for the PI to consider the grade of the event as well as its "seriousness" when determining whether reporting to the IRB is necessary.

6. Plan for reporting UPIRSOs (including Adverse Events) to the IRB

The principal investigator will report the following types of events to the IRB:

Any incident, experience or outcome that meets ALL 3 of the following criteria:

- 1. Is unexpected (in terms of nature, specificity, severity, or frequency) given (a) the research procedures described in the protocol-related documents, such as the IRB-

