An independent DSMC has been established to oversight the study. The members of the DSMC are as follow:

[name]
Professor of Medicine, Yale University

[name]
Professor of Medicine, Yale University

[name]
Professor of Medicine, New York University

The committee will meet within the 1st week after the study initiation to establish a reviewing plan and a standard operating procedure for what the rules are for stopping the study and how adverse events will be reviewed. In addition, the committee will meet as frequent as needed to review any emerging safety issues and adverse events and finally at the time of study closure. Minutes will be maintained.

The data monitoring committee will review all the data after half the subjects in the study are enrolled according to the stopping and continuance rules established by the Committee.

The committee recommendations will be communicated to other sites on a regular basis. The central PI, [name] will create a secured Yale Box for data and document transfer. A copy of the committee members' CV and qualifications will be kept in the master file.

The principal investigator (*[name]*) will conduct a review of all adverse events upon completion of every study subject. The principal investigator will evaluate the frequency and severity of the adverse events and determine if modifications to the protocol or consent form are required.

d. For multi-site studies for which the Yale PI serves as the lead investigator:

- i. How will adverse events and unanticipated problems involving risks to subjects or others be reported, reviewed and managed?
 - **Any perioperative and post-24hr clinical complications the PI at each center feels is directly related to deployment of the Bridge occlusion balloon must be reported to the PI, the local site IRB and Yale HIC.**
 - **The PI will evaluate any unanticipated problems, will submit it to the HIC immediately.**
 - **Any adverse events or complications will be communicated to the co investigators through the weekly emails.**

The anticipated risks:

- Sudden drop in arterial blood pressure.
- Venous stasis that can induce arrhythmias and/or cardiac arrest.
- Cerebral venous hypertension.
- Temporary facial edema or facial cyanosis (bluish discoloration of the face).

- Groin hematoma or bleeding.
- Thrombus within SVC.

There is a section in the data collection form to document any other unknown adverse events.

- ii. What provisions are in place for management of interim results?

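### The data list in Section V.3 makes the site PI's view of direct relatedness a condition for recording a complication, and the protocol does not reconcile this with its own rule to document all adverse events

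*Protocol*

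**What the plan says.** **Narrow wording.** In Section V.3, under the data to be collected, the only item on complications reads "Any perioperative and post-24hr clinical complications the PI at each center feels is directly related to deployment of the Bridge occlusion balloon". The first bullet of Section V.11.d.i uses the same words to define what sites must report to the PI, the local IRB and the Yale HIC.

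**Wide wording.** Section V.11.c, item 1, says: "All sites are required to document all the adverse events and complication in the data collection form with the site PI assessment". It adds that "the central PI will review all the adverse events and perioperative complication within 1 day of receiving the data collection form". Item 2 gives the monitor a matching task: "The study monitor will verify that all the adverse events, concomitant medications, and current illnesses are reported in accordance with the protocol". Item 3 assigns attribution: "Adverse events will be monitored for each subject participating in the study and attributed to the study procedures / design by the principal investigator". Its scale has five levels from definite down to the last, "Unrelated: Adverse event is clearly not related to investigational procedures(s)/agent(s". Under item 7 the principal investigator "will conduct a review of all adverse events upon completion of every study subject", and Section V.11.d.i ends its reporting bullets with "Any adverse events or complications will be communicated to the co investigators through the weekly emails". The same subsection notes that the form has a section for other, unknown adverse events. Section VIII, item a, lists follow-up information to establish whether any adverse event occurred.

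**What depends on it.** One secondary endpoint in Section V.3 is the absence of perioperative clinical sequelae related to occlusion of the SVC area. There is no control group, and lead extraction follows in the same session (step 17). The safety committee is to review all the data once half the subjects are enrolled (Section V.11.c, item 7).

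**The concern.** The site PI's opinion has two different roles. In the Section V.3 item it decides whether a complication belongs to the collected data at all. In Section V.11.c, item 1, it is a remark recorded beside an event that is already on the form.

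The difference matters because attribution is hard here. The balloon is inflated just before an extraction that has serious complications of its own, and no comparison arm shows what extraction alone would produce. The protocol answers this by giving attribution to one principal investigator using one scale. That works only if the events reach that person. If a site screens first, on a personal judgement of direct relatedness, the central judgement is made on a reduced set. The endpoint count and the committee's half-enrolment review inherit the reduction, and sites that read the protocol differently contribute events under different rules.

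**Working it through.** No arithmetic applies to the conflict itself, and the protocol states no figure to reproduce. The check is a comparison of texts.

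**1. The statements side by side**

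| Place in the protocol | Scope of events | Role of the site PI's opinion |
|---|---|---|
| V.3, data to be collected | Complications judged directly related to deployment | Condition for inclusion |
| V.11.d.i, first bullet | Same wording | Condition for reporting to the PI, local IRB and HIC |
| V.11.c item 1, site documentation | All adverse events and complications | Recorded with the event |
| V.11.c item 1, central review | All on the form | None |
| V.11.c item 3, attribution | Events in each subject, including unrelated ones | None; the principal investigator attributes |
| V.11.c item 7, review after each subject | All adverse events | None |
| V.11.d.i, form section for unknown events | Other adverse events | None stated |
| VIII item a, follow-up | Any adverse events | None |

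**2. Can a site obey both?** Yes. A site that documents everything under Section V.11.c also supplies what Section V.3 lists. A site that works from the Section V.3 item alone falls short of Section V.11.c. The two texts are therefore compatible in one direction only, and no sentence tells the site that the V.3 item is a subset.

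**3. Does another rule settle it?** The monitor checks that adverse events are reported as the protocol requires. Since the protocol holds both wordings, that standard points back to the question. No order of precedence is stated.

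**4. Which events could change the endpoint?** Let N be the number of events that central attribution would call related to occlusion if it saw every event, and n the number it would call related among those that pass a site filter. The second set is contained in the first, so n ≤ N. Central review can downgrade an entered event but cannot restore one that was never entered. Events that both site and centre would call unrelated do not matter for this endpoint. The events at risk are those the site thinks not directly related and the centre would call related.

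**5. Is such a disagreement plausible?** The two tests use different terms. The V.3 item asks about direct relation to deployment, the endpoint about relation to occlusion, and the attribution scale about relation to study procedures, with probable and possible levels below definite. As an illustration, thrombus within the SVC is a listed anticipated risk (V.11.d.i). Found after an extraction, it might be put down to the extraction by a site and rated possible by the centre.

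**6. Scale.** The target is 25 subjects over 8 sites (Section VII.1), so one affected subject is 1/25 = 4% of the target. The endpoint is worded as no sequelae, so one unrecorded event could change whether it is met. This shows the sensitivity of the endpoint; it does not estimate how many events would be lost.

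**The case against.** The strongest reply is that the Section V.3 list excludes nothing. It is visibly incomplete: it leaves out the blood gases of steps 1 and 15, the vital signs from 10 to 30 minutes, and the demographics and history of Section VIII. It stands in a section that asks for a lay summary. The mandatory rule is in Section V.11.c, which names the instrument, and the form is described as having an unfiltered place for other events. Coordinators are trained on data collection before enrolment (V.3), sites send source documents, and an independent monitor checks entries against them from each site's first subject. On this view the bullet merely names the data for an endpoint that is itself about related events.

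Much of this stands. A reader might infer that the study collects only related complications, or that the five-level scale could never be filled. The documents support neither: the list is not declared exhaustive, and Section V.11.c gives a wider route into the data. A reader might also infer that Section V.11.d.i contradicts the criteria for unanticipated problems in Section V.11.c, item 6, which include possibly related events. That does not follow either. The two govern different reporting steps, and meeting one does not release the principal investigator from the other.

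What the reply does not remove is the filter itself. The bullet is a data-collection item, the only one on complications, and its condition is a site-level opinion. If full capture was always intended, the condition serves no purpose there and can mislead a site that works from the list.

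**Conclusion.** The point holds as an unreconciled inconsistency with a one-sided risk, and it should be corrected. Taken together, the safety sections favour recording every event, so loss is possible but not certain. Its size cannot be derived from the protocol, and the data collection form, which might show how sites are actually prompted, is not among the documents.

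The direction is firm under two assumptions: that at least one site applies the Section V.3 wording when filling in the form, and that site and centre would sometimes judge relatedness differently. Any effect on the count of occlusion-related sequelae is then downward. The protocol makes no statistical claims (Section V.12), which limits the consequence to the descriptive safety result and the committee's view of it. In an uncontrolled study with an endpoint worded as none, that result still needs a complete record.

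**What to change.** In the Section V.3 list, delete the condition that the site PI must feel the complication to be directly related, and keep the time window. All perioperative and post-24hr complications are then recorded, as Section V.11.c, item 1, already requires. Keep the site PI's relatedness opinion as a field on the form, and leave attribution to the principal investigator on the five-level scale of item 3.

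In the first bullet of Section V.11.d.i, state that the directly related wording governs expedited reporting only and does not limit what is recorded or sent to the central PI.

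The cost is two edited bullets and a few more form entries per site. The record will also hold complications of the extraction itself, which the relatedness field and central attribution must separate, and the count may look less favourable.
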